Even after the initial spasms have subsided, Botox may aid in the prevention of contracture and help facilitate therapeutic stretching techniques by reducing the basal tone of the plantar flexors. Even at rest, muscles exert a baseline tone to maintain posture and joint position. By weakening or paralyzing the gastrocsoleus complex, there would be an imbalance in muscular tone in the lower leg pulling the foot into a more dorsiflexed position even at rest. This will also reduce voluntary and involuntary guarding during stretching exercises, thus improving the effectiveness of rehabilitation regimens.

**B.10 Summary:** Based on Botox's ability to reduce pain and postoperative muscular spasms while at the same time eliminating resting basal tone of the primary plantar flexors about the ankle, it is felt that intramuscular injections will be beneficial in aiding therapeutic stretching exercises which is essential for maintaining ankle range of motion. These exercises will be started approximately 2 weeks after the time of definitive fixation which is well within the 8-10 weeks of maximal effect seen with intramuscular botulinum toxin injections. Botulinum toxin injections have not only been shown to prevent the development in of contractures, but also used to treat contractures which have already formed. The purpose of this study is to evaluate the effect of Botulinum toxin A injections into the gastrocsoleus complex on ankle dorsiflexion after staged internal fixation of tibial plafond fractures. If Botulinum toxin A proves effective, this approach could have a significant impact on the practice and outcomes of orthopaedic surgery and will allow for treatment and prevention of equinus contracture without the morbidity associated with an additional surgical procedure.

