#### Exclusion Criteria

- Younger than 18 years of age.
- Significant traumatic brain injury or cognitive disability that would interfere with post-operative rehabilitation and study questionnaires.
- Nerve, vascular, or tendon injury of the lower leg: injury to the tibial or peroneal motor nerves, injury to the posterior tibial artery requiring repair, or laceration of tendons that are involved in plantar flexion or dorsiflexion of the ankle which require repair.
- History of prior lower extremity fracture to the tibia or ankle of the affected limb.
- Incarcerated patients.
- Patients unable or unwilling to return for follow-up examination.
- Pregnant or lactating patients.
- History of disease affecting the neuromuscular junction (ex: myasthenia gravis).
- Use of aminoglycoside antibiotics at the time of definitive fixation.
- Ipsilateral foot injury that will impair dorsiflexion exercises: Lisfranc injuries, fractures or dislocations of the talus, calcaneus, navicular, cuboid, cuneiforms, or metatarsals (phalanx fractures or dislocations will not be excluded).
- Patients receiving Botulinum Toxin A for other reasons.
- Patients with a known hypersensitivity to Botulinum toxin A.
- Gustilo Anderson type III B and C.
- Patients with a weight greater than 115 kg – to ensure proper injection locations.

- Patients taking non-depolarizing neuromuscular blocking agents (not including those used for general anesthesia).

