**Table 1: Botox Dosing by Weight**

45-55 kg:	140 U
55-65 kg:	170 U
65-75 kg:	200 U
75-85 kg:	230 U
85-95 kg:	260 U
95-105 kg:	290 U
105-115 kg:	300 U

At the completion of surgery, the gastrocsoleus complex will be injected in four locations (superior medial, superior lateral, inferior medial, and inferior lateral) prior to the application of short leg splint, per the recommendation of prior studies. At each injection site,  $\frac{1}{4}$  of the total dose of botulinum toxin A or normal saline will administered in approximately 0.5 ml injections. The use of EMG or other imaging modalities has been recommended to ensure accuracy of botulinum toxin injection at the target muscle motor end plates, however it is not necessary when injecting the gastrocsoleus complex, even in small children due to its large size and superficial location. The injection sites are illustrated in the figure 2 below:

[figure not shown]

Figure 2

Following definitive fixation and study injections, patients will be placed in a well-padded splint in at least neutral dorsiflexion for two weeks to allow for wound healing. Following wound healing, patients will transition to a removable orthosis and begin range of motion exercises and stretching techniques. All patients will undergo a structured exercise regimen. Each patient will receive a pamphlet at an 8th grade reading level containing a standardized exercise protocol which clearly states the exercises to be utilized, the frequency, and duration. As long as there are no adverse events, patients will proceed to touch down weight bearing at roughly 6 weeks postoperatively and continue their exercise program. Patients will then advance to partial weight bearing at approximately eight weeks and full weight bearing as tolerated at 10 to 12 weeks, as long as no adverse events occur precluding this progression.

Study participants will return to regularly scheduled follow-up appointments to monitor their progress. At each follow-up appointment (2 weeks, 6 weeks, 12 weeks, 6 months, and 1 year), patients will be monitored for signs and symptoms of Botox toxicity. All patients will be seen in follow-up at one of two clinic locations. At each site, research staff familiar with the study will be present along with a device for measuring dorsiflexion in a standardized fashion.

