#### **D.7 Potential Problems**

In a busy trauma center, the enrollment of patients in prospective randomized study can be difficult. We will train the attendings, fellows, residents, and our research staff to identify potential candidates for the study. Information about the study including the inclusion/exclusion criteria will be readily available online or on study information cards provided to the staff and residents. Additionally, all surgical staff will receive an in-service training session so that they are aware of the study protocol to be followed in the operating room. There will be approximately 14 days between the time of injury and definitive fixation giving ample time for patient identification and obtaining informed consent.

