##### **5.6.a.1 Botulinum Toxin Safety**

Botulinum Toxin A has been approved by the FDA for more than 20 years and has a long-established safety profile. When used correctly, the side effects of Botulinum Toxin type A injections are uncommon and usually mild and transient. Local side effects are the most common and are usually mild pain at the injection site and adjacent muscle weakness due to diffusion of the toxin across fascial barriers. Systemic side effects are very rare and include mild generalized weakness, urinary incontinence, constipation, and dysphagia; all of which are typically seen in susceptible individuals. Botox is contraindicated in patients with a history of neuromuscular disorder such as myasthenia gravis, and in patients receiving aminoglycoside antibiotics or non-depolarizing neuromuscular blocking agents, as these can all potentiate the effects of the toxin. It is also relatively contraindicated in patients with a history of pseudobulbar palsy and frequent chest infections for concern over aspiration pneumonia, an exceedingly rare, but serious side effect. These adverse events are not expected to cause problems based on our study design and patient population.

Of the local side effects, pain at the injection site is unlikely to be noticed by the patient as injections will be administered under general anesthesia and the patient's co-committent injury will likely dwarf any residual pain from the injection. The diffusion of Botox into adjacent muscle groups is not only inconsequential, but in-fact desired based on our study design. Although all injections will be made in the muscle belly of the gastrocnemius, diffusion into the deeper soleus muscle would provide additional weakness of the gastrosoleus complex and potentially result in better outcomes without causing additional functional impairment

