In order to minimize the occurrence of systemic side effects, the amount of Botox utilized in this study will be well below the maximum safe dose for Botox, 12U/kg, even if bilateral pilon fractures are both randomized to the treatment group. In addition, patients with a history of a neuromuscular disorder, who are receiving aminoglycoside antibiotics or non-depolarizing neuromuscular blocking agents, or women who are or may become pregnant will be excluded from this trial. Patients reporting dysphagia or aspiration are typically those undergoing injections for cervical dystonia, and may be considered a local side effect rather than a systemic one. Based on the remote injection site utilized for this study, dysphagia and aspiration are unlikely to be experienced. The average total dose of 200U of Botulinum Toxin A will be injected into the gastrocnemius of the effected extremity and was chosen based on the effective dose for the average gastrocnemius from other studies.

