#### **E.6.a.2 Duration of Botox**

An intramuscular injection of Botox results in flaccid paralysis that gradually improves over an average of 2 to 4 months. Although the effects are temporary, paralyzing the primary plantar flexors in the lower leg could prove problematic and result in gait disturbances contributing to subsequent falls. For this reason, pilon fractures have been chosen for this study because it is an injury which not only commonly results in ankle stiffness, but it also requires a non-weight bearing status for approximately 3 months, allowing the botulinum toxin to run its course without interfering with return to normal function. The effects of Botox are entirely reversible over time, and long term effects are unlikely to be experienced.

**E.6.b Foreseeable Benefits:** The specific aims of this study are to provide improved outcomes of operatively treated tibial plafond fractures by using Botox to improve ankle dorsiflexion. Patients randomized to the Botox arm of the study have the potential to experience increased ankle dorsiflexion, which will result in improved gait and lower limb functionality, as well as reduce the risk of developing other lower extremity pathologies.

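### The aminoglycoside exclusion stops at the operation where the toxin is injected, and the plan is silent on a later start (minor patient-safety improvement)

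*Combined protocol and SAP*

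**What the plan says.** Both exclusion lists, in D.1 and E.2, contain the same item: "Use of aminoglycoside antibiotics at the time of definitive fixation". Section 5.6.a.1 (Botulinum Toxin Safety) restates it among the steps to limit systemic effects: patients with a neuromuscular history, or "who are receiving aminoglycoside antibiotics or non-depolarizing neuromuscular blocking agents, or women who are or may become pregnant will be excluded from this trial". The same section gives the reason. The toxin is contraindicated, among others, "in patients receiving aminoglycoside antibiotics or non-depolarizing neuromuscular blocking agents, as these can all potentiate the effects of the toxin".

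D.3 places the study injections at the end of the definitive operation. On duration, B.10 describes the start of exercises at about 2 weeks as "well within the 8-10 weeks of maximal effect seen with intramuscular botulinum toxin injections", and E.6.a.2 states: "An intramuscular injection of Botox results in flaccid paralysis that gradually improves over an average of 2 to 4 months".

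After injection, D.3 provides for checks throughout scheduled follow-up ("2 weeks, 6 weeks, 12 weeks, 6 months, and 1 year), patients will be monitored for signs and symptoms of Botox toxicity"). D.2 lists deep and superficial infection, osteomyelitis, wound breakdown and rehospitalization as complications to be captured. E.7 appoints a data safety monitor, who is to be told of relevant adverse events within 24 hours and may unblind.

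**The concern.** The exclusion exists because the plan expects aminoglycosides to strengthen the toxin's effect. Yet it applies on the day the toxin is given and not afterwards, while the plan's own figures put the effect at weeks to months. The complications listed in D.2 make later antibiotic treatment foreseeable. Open fractures short of Gustilo-Anderson IIIB may also enter.

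A clinician treating an infection at week 5, say, is blinded to allocation and finds no instruction about this drug class. If an aminoglycoside is given, no item listed in D.2 would record it. What is at stake is the safety of an individual participant, and the ability to connect an event with its possible cause.

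**Working it through.** The plan gives no figure for this risk, so the main check is to set its statements side by side. The only arithmetic concerns timing and dose.

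1. **When the rule applies.** D.1 and E.2 tie it to definitive fixation. The wording in 5.6.a.1 has no time point, but it speaks of patients being excluded from the trial, which reads as an entry rule. D.3 puts the injection at the end of the same operation. The rule therefore covers day 0 and nothing stated covers later days.

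2. **How long the toxin acts.** Maximal effect (B.10): 8 × 7 = 56 to 10 × 7 = 70 days. Paralysis (E.6.a.2), with a month of 365.25/12 = 30.44 days: 2 × 30.44 = 61 to 4 × 30.44 = 122 days on average. No section says how long the interaction with aminoglycosides lasts. Taking 4 months as an outer bound is an assumption.

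3. **Whether any rule covers days 1 to 122.** Aminoglycosides are mentioned only in the two exclusion lists and in 5.6.a.1. D.3, D.7 and E.7 give no instruction about them. D.2 lists no concomitant-drug item. The case report forms are not in the documents, so they may hold a field that the protocol does not mention.

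4. **What the existing safeguards do.**
   - *Toxicity checks (D.3).* The visits at 2, 6 and 12 weeks (days 14, 42 and 84) fall within 122 days. They look for an effect after it has occurred; they do not prevent or record the combination.
   - *Information cards (D.7).* "Information about the study including the inclusion/exclusion criteria will be readily available online or on study information cards provided to the staff and residents". As described, these carry the entry criteria and so repeat the day-0 rule.
   - *Dose margin.* The highest dose per kilogram for the weights in Table 1 is at 45 kg: 140/45 = 3.11 U/kg. The top band gives 300/105 = 2.86 U/kg. If both legs are randomized to toxin, 2 × 3.11 = 6.22 U/kg. Against the 12 U/kg in 5.6.a.1 these are 3.11/12 = 26% and 6.22/12 = 52%. The margin is real, but no section says that the limit allows for potentiation, and the plan kept the exclusion despite it.
   - *Data safety monitor (E.7).* Only events beyond what is normal after trauma surgery are considered. E.7 gives generalized weakness and constipation as examples of effects common at baseline. Section 5.6.a.1 says: "Systemic side effects are very rare and include mild generalized weakness, urinary incontinence, constipation, and dysphagia". Two of those four are thus ones that E.7 may discount. E.7 also names difficulty with urination, which is not the same as incontinence, and it does not name dysphagia. Its list is open-ended, so this is an overlap and not a full count.

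5. **How many patients.** Ten are planned for toxin. The documents give no rate of aminoglycoside use after injection, so no expected number can be derived.

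**The case against.** A reader might infer that the plan permits a combination it calls contraindicated. The text does not go that far. Section 5.6.a.1 contraindicates giving the toxin to someone already receiving an aminoglycoside. It says nothing of an aminoglycoside started weeks after the toxin, and silence is not permission. The plan also exempts neuromuscular blockers used for general anesthesia, from a class named in the same sentence, so it does not treat every co-exposure as barred. Both points stand. They limit the finding to an omission. The anesthetic exemption is written down, however, whereas a later aminoglycoside start is not addressed at all.

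A reader might also infer that clinicians have no reason to treat participants as possibly exposed. D.3 has both arms checked for toxicity at every visit, so for monitoring they already do. What is missing is narrower: an instruction on antibiotics and a record of their use.

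Nor do the intervals between visits measure this gap. They would be the same for any adverse event and say nothing about aminoglycosides. The later part of the 4 months also lies beyond the stated period of maximal effect.

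The E.7 restriction applies with or without an antibiotic, and an unusually severe weakness could still pass it. It does not show that the exclusion is faulty. It does mean that the monitor is an incomplete backstop for this case.

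Finally, the 4-month window is assumed, systemic effects are described as very rare, and the trial is small. These points keep the matter minor. They do not remove it, because the correction is small too.

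**Conclusion.** The point holds as a minor patient-safety improvement. The plan states a potentiating interaction, ends its only rule on the day the toxin is given, and is silent on a start during the following weeks or months. Existing safeguards lower the risk without preventing or recording the combination.

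The number of patients affected is unknown and may be zero. The primary estimate and the error rate are not affected. The conclusion rests on reading 5.6.a.1 as an entry rule, and on there being no instruction or data field in study materials outside the documents. The proposed window further assumes that the 4 months given for paralysis is a reasonable outer bound for the interaction.

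**What to change.** - **D.3, study cards and in-service training:** for 4 months after injection, treating clinicians regard every participant as possibly exposed to toxin and avoid aminoglycosides where a suitable alternative exists. Needed infection treatment is not to be delayed. State that the 4 months is an assumed bound taken from E.6.a.2.
- **Visit forms at 2, 6 and 12 weeks and 6 months:** record any aminoglycoside start (drug, route, dates, reason) and tell the data safety monitor, within the 24 hours already used in E.7.
- **E.7:** in a participant so exposed, report weakness, bowel, urinary or swallowing events to the monitor even if they would otherwise count as expected. Exposure alone does not lead to unblinding. A single allocation is opened only if a toxin-type event occurs or the monitor judges it clinically necessary.

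The cost is a few sentences, one line on the cards, one extra form field, a few more reports to the monitor and possibly a rare single-patient unblinding. There is also a clinical cost: antibiotic choice is softly narrowed for all 20 participants, including the 10 on saline, who have no toxin to potentiate. That is why the instruction should be advisory and not a prohibition.

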## **D.2 Outcome Variables**

### ***Primary Outcome Variable (objective):***

Ankle Dorsiflexion of Injured Extremity. The primary outcome variable will be ankle dorsiflexion of the injured extremity as measured by a goniometer and radiographs.

Ankle Dorsiflexion of Uninjured Extremity. In patients with a unilateral lower extremity injury, the ankle dorsiflexion of the uninjured extremity will be measured in the same fashion as the injured extremity.

### ***Secondary Outcome Variables (self-report):***

The Short-Form 36 (SF-36) will be used to measure health related quality of life. The SF-36 is a commonly used general health status measure and assessment of function, which allows individuals to describe their own health status. It allows for the comparison between individuals with the same condition as well as to the general population. Subscale scores measure various domains of health and quality of life, while the physical (PCS) and mental (MCS) component summary scores represent the main dimensions of health. The PCS and MCS scores range from 0 to 100 points and are standardized to population norms with higher scores indicating higher function. The mean score for the PCS and MCS in the general population is 50 points with 10 points representing one standard deviation from the mean.

Pain. Overall Study limb as well as ankle specific pain intensity will be measured using the 0-10 visual analogue scale used in the Brief Pain Inventory. Pain intensity will be measured both at rest and during ambulation. The Brief Pain Inventory (BPI) will be administered to patients at 6 and 12-month follow-up appointments. The BPI is a widely used, 15-item measure of pain intensity and interference with daily life. The questionnaire assesses three key pain domains: pain intensity, pain interference, and efficacy of pain treatments or medications.

The Foot and Ankle Ability Measure (FAAM) is a well validated instrument that consists of 29 items measuring 2 broad categories: activities of daily living (84 points) and sports (32 points). The scores are normalized to 100 for each category and are reported separately. The FAAM will be obtained at 6 and 12 months to assess the functional status of the affected ankle.

### ***Independent Variables***

Group Assignment: Participants assigned to the control group will receive normal saline injections following definitive fixation of their tibial plafond fracture (N=10). Patients assigned to the treatment group will receive Botulinum toxin A injections following definitive fixation of their tibial plafond fracture (N=10).

### ***Covariates***

#### ***Demographics***

- Age
- Race/ethnicity
- Gender
- BMI

- Co-morbidities
- Fracture classification
- Time until definitive fixation
- Tobacco use
- Workers compensation status
- Level of education
- Marital status
- Personal income
- Health insurance
- Working status before injury

These data will be abstracted from the medical record by the research staff.

*Additional Outcomes*

- Time until full weight bearing
- Time until return to work
- Compliance with weight bearing status
- Compliance with prescribed treatment

These data will be patient reported

*Complications*

- Nonunion
- Malunion
- Infection: Deep
- Infection: Superficial
- Osteomyelitis
- Wound breakdown
- Skin slough: partial thickness
- Skin slough: full thickness
- Additional surgeries: Strayer recession, Achilles lengthening, hardware removal, amputation, or arthrodesis.
- Rehospitalizations

These data will be captured during clinical exam at each office visit

### **D.3 Methods**

Orthopaedic surgery attendings and residents will identify potential study candidates during the initial consultation based on the presence of a tibial plafond fracture. If the patient meets the inclusion and exclusion criteria (noted above), a member of the treatment team will discuss the study with eligible patients. If the patient expresses interest in the study, the physician will notify the research staff. Orthopaedic Clinical Research staff will describe study procedures in detail and go through the informed consent process to enroll the patient in the study. Patients will be informed of the “off-label” usage of botulinum toxin injections as well as the potential side effects.

Once informed consent is obtained and the patient is enrolled in the study, the attending surgeon will classify the fracture based on the AO/OTA classification system (Figure 1). Study participants will then be block randomized and assigned by sequentially numbered sealed opaque envelopes to one of the two treatment groups based on computerized selection: those who receive intramuscular botulinum toxin injections at the time of definitive fixation, and those who receive placebo. Patients with bilateral pilon fractures and no other lower extremity injuries of the tibia, ankle, or foot that would further impair dorsiflexion stretching or other

rehabilitation exercises will have each extremity randomized and evaluated separately. Patients with a unilateral tibial plafond fracture and no injury of the contralateral tibia, ankle, or foot will be placed in a subgroup of patients who will have their unaffected extremity examined for comparison. Patients with an injury to the contralateral extremity that would exclude them from this subset will have only the extremity with the pilon fracture analyzed.

[figure not shown]

Figure 1.

All patients will be treated by a fellowship trained orthopaedic surgeon who has completed advanced training in either trauma or foot and ankle surgery. Patients will all undergo a staged fixation approach which involves primary external fixation with irrigation and debridement if necessary, followed by open reduction and internal fixation when soft tissues allow. Additional procedures on the injured extremity that take place between external fixation and definitive fixation (ex: ORIF of the fibula or repeat irrigation and debridement) do not disqualify the patient from the study as long as definitive fixation takes place within 3 weeks (21 days) of the injury. All definitive operations will take place at either Carolinas Medical Center – Main, or Carolinas Medical Center – Mercy.

At the time of definitive fixation, the hospital's investigational pharmacy will provide a blinded solution of either Botulinum toxin A or 0.9% sodium chloride solution for injection intraoperatively following skin closure. Four syringes containing 0.5 ml 0.9% sodium chloride, with or without Botulinum toxin type A based on the patient's randomization, will be provided and refrigerated until they are ready to be administered. Both the physician and the patient will be blinded to the contents of the syringe. Once reconstituted, botulinum toxin type A will only last for 4 hours at room temperature so it will be necessary to not allow the solution to sit at room temperature for an extended period of time. All patients in the study group will receive onabotulinumtoxinA, Botox® (Allergan, Irvine, California) provided by the investigational pharmacy. The total dose of botulinum toxin will be calculated based on the patient's weight in kilograms, such that a total dose of 200U of Botox will be used for a 70 kg individual (see Table 1 below). The dosage will scale linearly in

proportion to the patient's body weight, such that each kilogram change results in a 3U change in Botox (rounded to the nearest 30U interval change from 200U, with a maximum of 300U). This dosing regimen was chosen based on the effective dose for an average gastrocnemius from other studies.

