## **D. Research Design and Methods**

We will use a prospective double-blind randomized placebo-controlled study design. Subjects will be enrolled as inpatients or during the initial office visit by orthopaedic clinical research staff. After routine evaluation reveals that a patient meets the inclusion and exclusion criteria (below), informed consent will be obtained. Demographic data will be recorded. Patients will be block randomized by opaque, sealed-envelope to either a treatment group or a placebo group (N=20; N=10 treatment, N=10 placebo).

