#### **D.4 Data Management**

All data will be entered into REDCap, a web-based data entry and management system that provides logic checks on input and checks for invalid entries. Data will be entered continuously as they are collected and stored in univariate form. We will also run standard checks for outliers, duplicates and other types of errors which may occur within a complex data file. All data files will be password protected and hard copies of blinded patient records will be maintained in locked cabinets in the research office.

*Data Analysis:* In order to determine that the randomization process produced comparable groups, we will use t-tests and cross-tabulations to compare patients in the treatment group to patients in the placebo group on the following variables: age, race, gender, BMI comorbidities, fracture classification, time until definitive fixation, tobacco use, workers compensation status, level of education, marital status, personal income, health insurance, working status before surgery, compliance with weight-bearing restrictions, compliance with prescribed treatment, time until full weight bearing and return to work.

Analyses will follow the intent-to-treat paradigm, under which all patients will be analyzed according to the treatment group to which they were randomized. Intention to treat analyses of outcomes will be conducted in two stages. First, we will conduct a bivariate analysis to examine relationships between assigned treatment

group, primary and secondary outcomes, and potential covariates and confounders (demographics, injury characteristics, co-morbidities). We will then use the results to build a multivariate model to predict primary and secondary outcomes based on treatment type.

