#### **E.5 Description of the Informed Consent Process**

Once a patient has expressed interest in the study, a member of the treatment team will provide each patient with sufficient time and information to make a well-informed decision on whether or not to enroll in the study based on the risks and benefits imposed. There are strong ethical and practical reasons for striving for quality in the consent process and is taken seriously by all those involved in this study. Decisions made hastily or without accurate and adequate information are not in the patient's or the investigators' interest. Materials to inform prospective participants and to obtain consent will be developed in conjunction with the Steering Committee and consultants as required to ensure that they are accessible, informative and culturally sensitive.

Persons who meet the initial eligibility criteria for the study will be told of the trial, its purpose, and the general expectations of those enrolled. Those interested in further screening and willing to participate will be given a copy of the consent. Formal consent, as represented by the act of signing and dating an IRB approved consent statement for the trial, will occur after the final evaluation for eligibility and a review of what is involved in the trial. Persons will be reminded of the expectations placed on them if they enroll. They will be advised not to enroll if they are uncertain that they would be willing to accept treatment as assigned by a random process. Ambivalent subjects should not be enrolled. Persons will be given an opportunity to query study personnel on issues needing clarification. Patients who no longer wish to be involved in the study will be withdrawn immediately at their request and continue to receive the standard of care.

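### Randomisation follows consent and fracture classification with no tie to the day of surgery, so patients who later become ineligible or are not injected can already be in an intent-to-treat arm of 10

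*Combined protocol and SAP*

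**What the plan says.** **Order of steps.** Section D enrols patients early: "Subjects will be enrolled as inpatients or during the initial office visit by orthopaedic clinical research staff". Section E.5 says that formal consent "will occur after the final evaluation for eligibility and a review of what is involved in the trial". Section D.3 continues: "Once informed consent is obtained and the patient is enrolled in the study, the attending surgeon will classify the fracture", and after that "Study participants will then be block randomized and assigned by sequentially numbered sealed opaque envelopes". No date is attached to the allocation step.

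**Injection.** D.3 has the investigational pharmacy supply blinded syringes at the time of definitive fixation. The injection follows skin closure. D.7 gives the usual interval: "There will be approximately 14 days between the time of injury and definitive fixation".

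**Conditions that look forward to surgery.** The exclusion list in D.1, repeated in E.2, includes "Use of aminoglycoside antibiotics at the time of definitive fixation". On the 21-day limit, the inclusion criterion in D.1 and E.2 describes a planned course of treatment. D.3 says that interval procedures "do not disqualify the patient from the study as long as definitive fixation takes place within 3 weeks (21 days) of the injury".

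**Analysis.** Under D.4, "all patients will be analyzed according to the treatment group to which they were randomized". The documents describe no eligibility check on the day of surgery, no rule for a patient randomised but not injected, no modified analysis set and no replacement rule.

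**Use of the pilot.** Section A concedes that 20 patients will probably be too few to settle the aims. D.5 and D.8 use the pilot data for the full-trial power analysis. D.8 pools them with the full cohort if the protocol is unchanged.

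**The concern.** At least one exclusion is defined by what happens at definitive fixation, yet the last described eligibility evaluation comes before consent and allocation follows consent. A patient can pass every check, be allocated, and then meet an exclusion before the injection. The safety section lists aminoglycosides as a contraindication because they can potentiate the toxin, so such a patient may well go uninjected. The plan does not say what happens then.

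Keeping all randomised patients in their arms is the right analysis. The weakness is that the sequence can create avoidable uninjected patients. With 10 per arm, each is a tenth of the arm. The harm falls mainly on the estimated difference and its use in planning, because the pilot is not meant to be decisive.

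**Working it through.** **Inputs from the documents.** 20 patients, 10 per arm (Section D). About 14 days from injury to fixation (D.7). A 21-day limit (D.1, D.3). Significance at p < 0.05 (end of D.3).

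**Inputs that are assumptions.** Two-sided testing; the spread of time to fixation; a true effect of 1 SD; an uninjected patient behaves like a control. The documents give no effect size, SD, power, late-ineligibility rate or rate of aminoglycoside use. The pilot size of 20 therefore cannot be reproduced from a power calculation.

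**Step 1: the gap.** Consent can fall at any time between presentation and surgery. With fixation at about day 14, the gap from allocation to injection runs from near 0 to about 14 days.

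**Step 2: effect of one uninjected patient.** If k of the 10 treatment-arm patients are not injected, the expected intent-to-treat difference is (10 − k)/10 of the full effect. For k = 1 it is 0.9, a loss of 10%. Required sample size varies as 1/(effect)², so a full trial planned on that estimate is larger by 1/0.9² = 1.235, or 23%.

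**Step 3: an illustrative rate.** Take time to fixation as Normal with mean 14 and SD between 4 and 7 days.

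- SD 4: P(T > 21) = P(Z > 7/4) = 0.040
- SD 7: P(T > 21) = P(Z > 7/7) = 0.159

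Over 20 patients this is 20 × 0.040 = 0.8 to 20 × 0.159 = 3.2. Only treatment-arm patients dilute the difference. Split evenly, that is 0.4 to 1.6 of the 10 treated.

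**Step 4: power if every one of them went uninjected.** Two-sample t test, 10 per arm, 18 degrees of freedom, two-sided 0.05, noncentrality d × √(10/2).

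| Uninjected treated patients | Diluted effect d (SD) | Power |
|---|---|---|
| 0 | 1.00 | 56% |
| 0.4 | 0.96 | 53% |
| 1.6 | 0.84 | 43% |

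**Limits.** At SD 7 the Normal model puts P(Z < −14/7) = 2.3% of fixations before the injury, so the upper end is crude. The model ignores that patients are enrolled because fixation within 21 days is planned, which may make lateness rarer. It leaves out aminoglycoside use, which has no stated rate.

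**The case against.** The strongest reply is that D.3 gives an order and not a date. A reader might infer that patients are randomised immediately after consent, routinely two weeks before injection. The documents do not say so, and opening the envelope close to surgery is compatible with the text. This stands: early allocation is permitted, not shown.

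A reader might also count two conditions that can be known only on the day of surgery. Only the aminoglycoside exclusion is clearly tied to that time. The inclusion criterion words the 21-day limit as a plan, which can be judged at enrolment. The D.3 clause is chiefly about interval procedures, and passing day 21 is known before a late operation begins. This also stands.

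Nothing says that a patient fixed after day 21 goes uninjected. A late patient who is injected causes no dilution of the kind computed here, so the lower powers describe a worst case. Nor does any text say that randomised patients would be removed; D.4 says the opposite, and only the mention of disqualification in D.3 hints at it.

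An estimate that includes non-receipt is arguably the right planning input if the full trial runs in the same manner, as D.5 intends. That is fair, but the full trial would then be enlarged to absorb a loss that a change of timing could avoid. The step could be changed after the pilot, but D.8 allows pooling only if the protocol is unchanged.

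Finally, a reader might infer that early envelopes expose the allocation to the research staff at the dorsiflexion visits. The documents do not say who opens envelopes or that those staff learn the allocation, so this is no part of the point.

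**Conclusion.** The concern holds in limited form. The stated sequence allows allocation before eligibility at surgery is settled, describes no re-check, and leaves patients randomised but not injected without a handling rule beyond the as-randomised analysis. That rests on the text alone.

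The size is conditional. The loss of about 10% of the expected difference per uninjected treatment-arm patient needs only the assumption that such a patient behaves like a control. The fall in power from 56% to between 53% and 43% also depends on an assumed spread of fixation times, an assumed 1 SD effect, and every late treatment-arm patient going uninjected. It illustrates scale and does not forecast. In an admitted pilot the practical consequence is a smaller planning estimate. The change is worth making because it is cheap, not because a large loss has been shown.

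**What to change.** In D.3, keep consent and fracture classification where they are. Open the next envelope on the day of definitive fixation, as close to the injection as practical, after the existing eligibility criteria are re-confirmed. The investigational pharmacy then prepares the syringes from that allocation. A patient who fails the check is a screen failure and uses no envelope.

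In D.4, add that any patient randomised but not injected stays in the intent-to-treat set and is reported by arm with the reason.

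The sponsor should also reconcile D.1 and E.2 with D.3 on whether the 21-day limit is an intent at enrolment or a condition for remaining in the study.

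The cost is a few sentences and same-day coordination with the pharmacy at the two hospitals where definitive operations take place. No extra patients or visits are needed. Exposures that begin during surgery, after the check, would still be missed, so the reporting rule is needed in any case.
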